11.2 Record Retention

In accordance with FDA regulations, the investigator shall retain records for a period of 2 years following the date a marketing application is approved for the drug for the indication for which it is being investigated; or, if no application is to be filed or if the application is not approved for such indication, until 2 years after the investigation is discontinued and FDA is notified.

12 Statistical Considerations

12.1 Statistical Analysis Plan

- **12.1.1 Primary Safety Objective:** Evaluate the incidence and severity of adverse events associated with the treatment regime. The proportion of patients experiencing Regimen Limiting Toxicity (RLT, Section 5.3.1) in each arm will be tabulated with 95% exact (Clopper-Pearson) confidence intervals. The proportions of patients experiencing RLT will be compared between arms by the Fisher's exact test. The power of this test is described in Section 12.3. The early stopping rule for RLT is described in Section 12.2.
- **12.1.2 Primary Immunogenicity Objective:** Detection of vaccine-induced immune response in pre- and post-vaccine PBMC. The standardized difference between pre- and post-vaccine PBMC will be compared between arms via a two-sample Student's *t* test. We assume the magnitude of difference will be greater in Arm 1 than Arm 2. If the *t* test assumptions are not met and the data cannot be transformed in such a way that the assumptions are met, a Wilcoxon Rank Sum test will be used. Based on a one-sided two-sample equal variance t-test, the statistical power will be 80% with 15 patients per arm if the difference between arms is at least 0.8 with a standard deviation for both arms of 1.0 with a significance level of 0.10.
- **12.1.3 Exploratory Efficacy Objective:** Evaluation of IMA950-reactive T-cell infiltration and CXCL9/10 expression in tumors resected from Arm 1 and Arm 2 patients. In surgically resected tumor tissues from Arm 1 (IMA950+poly-ICLC and varlilumab) and Arm 2 (IMA950+poly-ICLC alone) patients, we will evaluate numbers of tumor-

12 April 2020 Page 75 of 88 confidential

- infiltrating CD4⁺ T-cells CD8⁺ T-cells (by flow-cytometry) and CXCL10 expression (by RT-PCR). This comparison will be made via two-sample t-tests unless the assumptions are not met then a Wilcoxon alternative will be employed.
- 12.1.4 Exploratory Efficacy Objective: To evaluate IMA950-reactive TCR clonotypes in tumors resected from Arm 1 and Arm 2 patients. Our expectation is to see a higher number of copies of vaccine-specific TCRs (frequency/total tumor DNA) in Arm 1 samples than in Arm 2 samples. This comparison will be made via two-sample t-tests unless the assumptions are not met then a Wilcoxon alternative will be employed.
- **12.1.5 Exploratory Efficacy Objective:** To estimate overall survival (OS) and progression-free survival (PFS) in the two arms. Product limit (Kaplan-Meier) estimates of the OS and PFS functions will be calculated with 95% Greenwood confidence regions. The trial is not adequately powered for the log-rank test that compares survival functions between arms.
- **12.1.6 Exploratory Efficacy Objective:** Evaluation of PBMC responses against IMA950 in association with OS, PFS and frequency of IMA950 reactive T-cells in the tumor. The association of the immunological parameter with PFS and OS will be evaluated using proportional hazards (Cox) regression. Frequencies will be tabulated.
- **12.1.7 Exploratory Efficacy Objective:** Tabulate tumor objective response rate (ORR). The (multinomial) distributions of responses in patients with measurable tumors (Section 9.2.3) will be calculated with simultaneous (Sison & Glaz) confidence regions. The trial is not adequately powered for a comparison between arms using Fisher's exact test.
- **12.1.8 Exploratory Efficacy Objective:** Evaluation of leukocyte phenotypes in PBMC samples. Frequencies will be tabulated to compare the distributions of the phenotypes between arms.
- **12.1.9 Exploratory Efficacy Objective**: Evaluation of pharmacokinetics for varlilumab. The purpose of this exploratory efficacy objective is to capture minimum and maximum values for the different pharmacokinetics measures. The purpose is not testing hypothesis; therefore descriptive statistics will be reported.

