1.1 Primary Objectives

We will evaluate our hypothesis that addition of agonist anti-CD27 monoclonal antibody varlilumab will enhance induction of effector T-cell response against antigens in IMA950 vaccine in patients with WHO grade II low-grade glioma. There are 2 co-primary endpoints:

- **1.1.1 Safety**: We will evaluate the incidence and severity of adverse events associated with the treatment regime, with an early stopping rule based on the frequency of Regimen Limiting Toxicity (RLT).
- **1.1.2 Immunological Activity**: We will determine the response rate and magnitude of CD4⁺ and CD8⁺ T-cell responses against the IMA950 peptides in pre- and post-vaccine PBMC using a novel, flow-cytometry-based 2D *ex vivo* assay system. We will determine whether Arm 1 patients demonstrate higher response rate and/or magnitude of response compared with Arm 2 patients.

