12.2 Stopping Rule for Toxicity

The trial will be stopped for toxicity if the number of patients experiencing RLT in either arm is excessive. A probability of RLT (pRLT) exceeding 0.33 would be considered prohibitively high. Based on the previous experience in UPCI 07-057 and UPCI 08-135, we believe the expected pRLT is 1/20, and that the probability pRLT is equal to or greater than 0.33 is 0.05. We will use a continuous Bayesian beta-binomial monitoring rule: stop the trial if the estimated P(RLT>0.33)>0.33. We will use a beta prior distribution with

12 April 2020 Page 76 of 88 confidential

[figure not shown]
parameters α =0.09 and β =1.71, representing our beliefs above. The stopping rule is specified in the table.

# Patients	# RLT	# Patients	# RLT	
3	2	12	4	
4	2	13	5	
5	2	14	5	
6	3	15	5	
7	3			
8	3			
9	3			
10	4			
11	4			

Stopping rule for toxicity: for the given number of patients in the either arm, the trial is halted if the number of RLTs equals the given number

[figure not shown]
The operating characteristics of this rule were determined by Monte Carlo simulation and are displayed in the graph. It is seen that if the true pRLT>0.33, the expected number of patients enrolled is five and the probability the trial stops early is 0.75, but if the true pRLT=0.1, the probability the trial stops early equals 0.2.

12 April 2020 Page 77 of 88 confidential

Operating characteristics of the stopping rule. The blue line is the expected number of patients in the trial (left axis) and the red line is the probability the trial stops early (right axis) as a function of the true (unobserved) pRLT.

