12.3 Justification of Design

The statistical power of the trial for the safety primary objectives is displayed in the plot.

12 April 2020 Page 78 of 88 confidential

For the primary safety endpoint, the power of the comparison of P(RLT) between the two arms is presented in terms of the arithmetical difference in the true P(RLT).

13 Budgetary Considerations

Neither subjects, nor their insurance provider, will be charged for the costs of any of the procedures performed for the purpose of this research study. Subjects will be charged, in the standard manner, for any procedures performed for their routine medical care (clinic visits, physical examinations, and laboratory tests to measure blood counts and chemistries). All MRI scans obtained will be considered standard of care for the management of a patient with WHO grade II glioma and will be billed to the patient's insurance provider. Subjects will be responsible for any costs for routine care not covered by their insurance provider, including any applicable co-payments, co-insurances and deductibles.

12 April 2020 Page 79 of 88 confidential

14 References

Reference List

- 2. van den Bent MJ, Wefel JS, Schiff D, et al: Response assessment in neuro-oncology (a report of the RANO group): assessment of outcome in trials of diffuse low-grade gliomas. The Lancet Oncology 12:583-593, 2011
- 4. The Central Brain Tumor Registry of the United S: Statistical Report: Primary Brain Tumors in the United States, 1998-2002, 2005
- 8. Ohgaki H, Kleihues P: Epidemiology and etiology of gliomas. Acta Neuropathol.(Berl) 109:93-108, 2005
- 9. Ohgaki H, Kleihues P: Population-based studies on incidence, survival rates, and genetic alterations in astrocytic and oligodendroglial gliomas. J.Neuropathol.Exp.Neurol. 64:479-489, 2005

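### The between-arm Fisher test of RLT, part of the co-primary safety analysis, is justified by a power that does not mention the toxicity stopping rule; if Section 12.2 halts the whole trial, little of that power remains

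*Combined protocol and SAP*

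**What the plan says.** Section 1.1 states: "There are 2 co-primary endpoints". Safety is one of them. Section 12.1.1 plans RLT proportions per arm with Clopper-Pearson 95% intervals and adds: "The proportions of patients experiencing RLT will be compared between arms", by Fisher's exact test. It continues: "The power of this test is described in Section 12.3".

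Section 12.3 reads: "The statistical power of the trial for the safety primary objectives is displayed in the plot". The caption says that power is plotted against the difference in true RLT probability. The plot is not in the text available for review. Neither section gives an alpha or a sidedness for this test. The only level in Section 12.1 is one-sided 0.10, for the immunogenicity t-test, where "the statistical power will be 80% with 15 patients per arm".

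Under the Section 12.2 table, "for the given number of patients in the either arm, the trial is halted if the number of RLTs equals the given number". The counts are 2 RLTs at 3–5 patients, 3 at 6–9, 4 at 10–12 and 5 at 13–15. Section 4.1 has a different consequence: two or more RLTs in the Arm 1 lead-in make that arm intolerable, and the study goes on with Arm 2 alone.

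Sections 12.1.5 and 12.1.7 admit inadequate power for the log-rank test and for the Fisher test of response. The RLT comparison carries no such caveat.

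**The concern.** The differences in RLT that the Fisher test should detect are the ones that trigger the stopping rule. A toxic Arm 1 ends enrolment while the samples are too small for the test, and an Arm 1 that gets through has too few RLTs. A power curve for a fixed 15 v 15 sample would therefore not describe this trial.

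What is at stake is interpretation. A non-significant p-value from a co-primary analysis with a power statement behind it can be read as showing that varlilumab adds no RLT. In most scenarios that result was likely whatever the true difference.

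**Working it through.** **Inputs.** From the plan: 15 per arm (12.1.2); the 12.2 table with its Beta(0.09, 1.71) prior; expected RLT rate 1/20, used for Arm 2; rates above 0.33 prohibitive (12.2); 1:1 allocation after the lead-in (4.1). Assumed: two-sided 0.05, with one-sided results also shown.

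**Plan's own figures.** The prior mean is 0.09/1.80 = 0.05, and P(p>0.33) = 0.050, as stated. Halting when the posterior P(p>0.33) exceeds 0.33 gives all 13 table entries. One arm at a true rate of 0.33 halts with probability 0.76 (stated 0.75). The stated expected enrolment of five is not reproduced (7.8 per arm), but nothing below depends on it. The t-test power comes to 0.81 (stated 80%). The Fisher power cannot be reproduced because it exists only in the plot.

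**Completed 15 v 15 trial.** The count at 15 patients is 5, so an arm that has not crossed has at most 4 RLTs. The most extreme split is 4/15 v 0/15:
- one-sided p = C(15,4)/C(30,4) = 1365/27405 = 0.0498
- two-sided p = 2 × 0.0498 = 0.0996

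The smallest significant split with no RLT in the other arm is 5/15 v 0/15: 2 × 3003/142506 = 0.042. Five is itself a halting count.

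**Halted trials with equal arms** (two-sided p): 2/3 v 0/3, 0.40; 3/6 v 0/6, 0.18; 3/9 v 0/9, 0.21; 4/12 v 0/12, 0.093; 5 v 0 at 13–15 per arm, 0.039–0.042.

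**Power**, Arm 2 rate 0.05, two-sided 0.05. Fixed power is by full enumeration and completion by exact recursion; the other rows are simulated, testing at the halt or at completion.

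| Arm 1 rate | 0.33 | 0.40 | 0.50 | 0.60 |
|---|---|---|---|---|
| Fixed 15 v 15, no stopping | 0.35 | 0.52 | 0.74 | 0.89 |
| 12.2; 3 Arm 2, 3 Arm 1, then alternating | 0.016 | 0.013 | 0.007 | 0.002 |
| 12.2; 3 Arm 2, 3 Arm 1, then random | 0.024 | 0.024 | 0.014 | 0.005 |
| 12.2; random order throughout | 0.037 | 0.044 | 0.049 | 0.069 |
| 12.2; delayed RLT onset | 0.11 | 0.12 | 0.09 | 0.055 |
| 4.1 followed, Arm 2 filled to 15 | 0.25 | 0.32 | 0.42 | 0.52 |
| Probability that both arms complete under 12.2 | 0.235 | 0.112 | 0.027 | 0.004 |

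The first three 12.2 rows assume each RLT is known before the next patient enters. The delayed row assumes 1.5 patients a month after the lead-in and onset uniform over 8 months. The 4.1 row applies 12.2 after the lead-in; other ways of coding the lead-in bring the top of its range to about 0.56.

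**Why 4.1 differs.** If Arm 1 closes at two RLTs and Arm 2 fills, unequal samples can be significant: 2/3 v 0/15 gives C(3,2)/C(18,2) = 3/153 = 0.020, and 2/4 v 0/15 gives 6/171 = 0.035.

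**Other levels.** At one-sided 0.10, fixed power is 0.61 / 0.77 / 0.91 / 0.97, against 0.12 / 0.13 / 0.15 / 0.19 under 12.2 with the alternating order and 0.47 to 0.71 under 4.1. At one-sided 0.05, 4/15 v 0/15 just passes, but rejection in a completed trial has probability at most about 0.03.

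**The case against.** The best defence is that a clearly toxic Arm 1 is caught by the stopping rule. At 0.50 v 0.05 both arms complete in under 3% of trials, and the halt is the detection. Safety conclusions rest on the 33% criterion, the stopping rules and the per-arm intervals; no decision hangs on the Fisher p-value. This stands, and it rules out calling the flaw a danger to patients. It does not justify a power claim for the test. Nor does it cover smaller differences: at 0.20 v 0.05 about 60% of trials complete, and even fixed power is only 0.08.

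A reader might infer four stronger things that the documents do not support:
- **That significance is impossible.** The level is unstated, and 4/15 v 0/15 passes at one-sided 0.05 or 0.10. Section 4.3 keeps replaced patients in the safety set, so an arm can exceed 15, where the table is silent; 5/16 v 0/15 gives p=0.043. RLTs can also arise after accrual ends. With the Bayesian rule extended past 15, replacement lifts completed-trial power only to about 1.2%.
- **That the plotted power is wrong.** The plot is not visible and might allow for stopping, so no overstatement can be measured.
- **That the Section 4.1 lead-in lowers power further.** Followed literally, it raises power.
- **That Section 12.2 should be the only safety rule.** That would override the closures in 4.1 and the enrolment halts in 5.6.2.

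**Conclusion.** The concern holds in a conditional form. If Section 12.2 halts the whole trial, the Fisher comparison keeps little of its fixed-sample power: 0.35–0.89 falls to roughly 0.002–0.07 with RLTs known at once, depending on enrolment order, and to about 0.1 with delayed onset. A completed 15 v 15 trial without replacements or late RLTs cannot reach two-sided 0.05. If Section 4.1 governs instead, power is about 0.25–0.56, but it comes from setting a handful of non-randomised lead-in patients against a full Arm 2, which is not the randomised comparison that the power statement implies.

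These figures rest on an Arm 2 rate of 0.05 and an assumed two-sided 0.05. With Arm 2 at 0.10 and Arm 1 at 0.33, fixed power is 0.20, and 0.01–0.02 under 12.2. Whichever section governs, the plan should not offer this test as a powered safety comparison without stating its level and accounting for stopping. This is a fault of inference and reporting, worth correcting but short of critical.

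**What to change.** - **Section 12.1.1:** report the difference in RLT proportions (Arm 1 minus Arm 2) with an exact 95% confidence interval, labelled descriptive, beside the planned Clopper-Pearson intervals. State that a non-significant comparison is not evidence of equal toxicity.
- **Section 12.3:** remove the Fisher power justification. Alternatively, restate it from a simulation that includes the stopping rules, with alpha, sidedness, enrolment order and RLT timing given.
- **Sections 4.1 and 12.2:** they disagree on whether excess RLTs in Arm 1 stop the whole trial or only that arm. The sponsor must reconcile them. The safety rules in 4.1, 5.6.2 and 12.2 stay in force meanwhile.

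The statistical cost is a few sentences and, if power is kept, one simulation. The restated power will probably look weaker than a fixed-sample curve. Reconciling 4.1 with 12.2 needs a protocol decision as well as an edit.

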- Uncontrolled intercurrent illness including, but not limited to ongoing or active
 infection (e.g. active or chronic hepatitis B and C), symptomatic congestive
 heart failure, unstable angina pectoris, or psychiatric illness/social situations that
 would limit compliance with study requirements

	 History or current status of immune system abnormalities such as hyperimmunity (e.g., autoimmune diseases) that needed to be treated by systemic therapy, such as immuno-suppressants and hypoimmunity (e.g., myelodysplatic disorders, marrow failures, AIDS, transplant immunosuppression). Receiving ongoing treatment with immunosuppressive drugs, or 		
	dexamethasone > 4mg		

Pilot randomized pre-surgical evaluation of varillumab on IMA950 vaccine plus poly-ICLC in patients with WHO grade II low-grade glioma

- 1) Arm 1: Patients will receive IMA950+poly-ICLC and CDX-1127
- 2) Arm 2: Patients will receive IMA950+poly-ICLC.

Drugs included in the current regimen are: 1) IMA950 peptides; 2) poly-ICLC and 3) CDX-1127. IMA950 and poly-ICLC will be administered as one formulation containing 4.96 mg total IMA950 peptides and 1.4 mg poly-ICLC subcutaneously (s.c.) at sub-inguinal sites. CDX-1127 will be administered intravenously (i.v.) at 3 mg/kg

Pre-surgical phase:

On days -23±2, -16±2, -9±2 and -2 relative to the scheduled surgery: All patients receive s.c. injections of IMA950/poly-ICLC vaccine. The 4th dose of pre-surgery IMA950/poly-ICLC vaccine must be administered between 24-48 hrs prior to scheduled surgery. PBMC sample (60-80 mL/draw) is obtained on the day of the 1st vaccine (on day -23±2); also at the D-23±2 visit, PK samples (1 x 10 cc red top tube/draw) will be collected prior to varlilumab administration and 30 minutes (±5 minutes) after the infusion has ended. For Arm 1 patients, Varlilumab (CDX-1127) will be administered i.v. on the day of the first vaccine immediately following the s.c. vaccination.

Surgery: The resected tumor tissue will be sent to the BTRC tumor bank.

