We recently completed a bi-institutional pilot study of s.c. vaccinations with synthetic peptides for GAA epitopes and the tetanus toxoid peptide emulsified in Montanide-ISA-51 every 3 weeks for 8 courses, and i.m. administration of poly-ICLC in human leukocyte antigen (HLA)-A2⁺ patients with: newly diagnosed high-risk LGG without prior RT (UPCI 07-057: Cohort 1); newly diagnosed high-risk LGG with prior RT (UPCI 07-057: Cohort 2); and recurrent LGG (UPCI 08-135). Primary endpoints were safety and CD8⁺ T-cell responses against vaccine-targeted GAAs, assessed by Enzyme-Linked Immuno-SPOT (ELISPOT) assays. Treatment response was evaluated clinically and by MR imaging. Targeted GAAs were EphA2, IL-13Rα2, survivin, and WT1.

In the UPCI 07-057 study, high-risk subsets of these LGG patients are defined as astrocytoma or oligoastrocytoma histology plus any one of the following conditions: 1) age ≥40 with any extent resection; 2) age 18-39 with incomplete resection; or 3) age 18-39 with neurosurgeon-defined gross total resection with tumor size ≥ 4 cm in diameter. We enrolled 13, 1 and 10 patients in UPCI 07-057 Cohorts 1, 2 and UPCI 08-135, respectively. No dose-limiting non-CNS toxicities have been encountered except for one case with Grade 3 fever (UPCI 07-057: Cohort 1). ELISPOT assays demonstrated robust IFN-γ responses against at least 3 of the 4 GAA epitopes in 10 and 4 cases of Cohorts 1 and 3, respectively. Cohort 1 patients demonstrated significantly higher IFN-γ responses than Cohort 3 patients.

Median progression-free survival (PFS) periods since the 1st vaccine was 17 months in Cohort 1 (range 10-47+) and 12 months in Cohort 3 (range 3-41+). Only one patient with a large astrocytoma in Cohort 2 has been progression-free for over 67 months. Although further follow-up is required to mature PFS data, our results demonstrate that the regimen in these patients is well tolerated, and induces robust type-1 anti-GAA T-cell responses. These data also suggest that patients with LGG are suitable for vaccine therapy.

12 April 2020 Page 22 of 88 confidential

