4.1 Registration and Randomization

Eligible patients will be entered on study at UCSF by the Study Coordinators. All patients who sign the informed consent document will be registered in OnCore and the Brain Tumor Research Center Tissue Bank database.

Arm 1: Patients will receive IMA950- poly-ICLC vaccine plus varlilumab. **Arm 2**: Patients will receive IMA950- poly-ICLC vaccine alone.

The study is designed with a staggered safety lead-in with the first 3 patients assigned to Arm 2. The first 3 patients of the study will be enrolled in Arm 2 in a staggered manner as follows. After the first patient of the study is enrolled in Arm 2, Patient number 2 and 3 will not be enrolled until the previous patient receives 4 pre-surgery vaccines and recover from clinically indicated surgery for at least 6 weeks after surgery without a regimen-limiting toxicity (RLT) to confirm the safety of IMA950-poly-ICLC vaccine.

If any of the first 3 patients on Arm 2 shows a RLT (see definition in section 5.3), an additional 3 patients (patients 4, 5 and 6) will be enrolled in the same, staggered manner in Arm 2 while Arm 1 enrollment is held. If 2 or more of the patients on Arm 2 show a RLT, the arm will be considered intolerable and the study will be closed. If only one total of the 6 patients shows an RLT in Arm 2, the randomized design will be cancelled and the study will proceed with Arm 2 only to primarily evaluate the safety of the Arm 2 regimen. When the study is completed with the total evaluable 15 patients in Arm 2, we will review the safety data, and discuss with the FDA and IRB regarding the extension of the study to Arm 1.

If none of the first 3 patients treated on Arm 2 demonstrates a RLT, then 3 further patients will be enrolled in Arm 1 (with varlilumab) in the same staggered manner (subsequent patients will not be enrolled until the respective previous patient receives 4 pre-surgery vaccines and recover from clinically indicated surgery for at least 6 weeks after surgery without an RLT to confirm the safety of IMA950-poly-ICLC-varli treatment. If one of first 3 patients on Arm 1 shows a **Regimen Limiting Toxicity** an additional 3 patients will be enrolled in the same, staggered manner in Arm 1. If 2 or more of the patients on Arm 1 show a RLT, the arm will be considered intolerable.

12 April 2020 Page 27 of 88 confidential

If Arm 2 is tolerable but Arm 1 is not, then, the study will be carried out with Arm 2 only.

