If both arms are found tolerable, then subsequent patients will then be randomized into one of the two arms for the pre-surgical part of the study. **Arm 1**: Patients will receive IMA950-poly-ICLC vaccine plus varlilumab. **Arm 2**: Patients will receive IMA950-poly-ICLC vaccine alone. The randomization will take place in a 1:1 ratio between the two arms with the stratification based on whether the patient is newly diagnosed vs. recurrent.

Patients will be assigned to treatment by means of the UCSF Biostatistics Facility randomization system in an open label fashion. Information on the two arms will be loaded into the database and the treatment arm assigned to the subjects when the subject's initials and ID# are entered into the program. Results of randomization will not be blinded, and no placebo will be used.

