8.1 Immunological Monitoring of PBMCs

Analyses of immune responses in PBMC will allow non-invasive evaluation of vaccine-induced immune response. As one of two co-primary endpoints of the current study, we will determine the response rate and magnitude of CD4+ and CD8+ T-cell responses against the IMA950 peptides in pre- and post-vaccine PBMC using a novel, flow-cytometry-based 2D *ex vivo* assay system. We will determine whether Arm 1 patients demonstrate higher response rate and/or magnitude of response compared with Arm 2 patients.

As the primary method of PBMC analysis, we will use a novel 2D multimer staining-based assays. ⁸³ The use of fluorescently labeled MHC multimers has become an essential technique for analyzing disease- and therapy-induced T-cell immunity. However, limitations on available PBMCs from patients preclude a comprehensive analysis of T-cell immunity. To address this issue, Hadrup et al. developed a combinatorial encoding strategy that allows the parallel detection of a multitude of different T-cell populations in a single sample (2D multimer staining-based assays). ⁸³ Detection of T-cells from PBMC by combinatorial encoding is as efficient as detection with conventionally labeled multimers but results in a substantially increased sensitivity and, most notably, allows comprehensive screens to be performed. We have confirmed that we can detect increases of IMA950-specific T-cells using PBMC samples obtained from GBM patients receiving IMA950 vaccines.

As the primary method to evaluate the relative immune response levels between two Arms, the relative magnitude of responses against each of IMA950 antigens will be compared between two Arms by comparing the sum of post-vaccine tetramer+ percentages of all time points from all patients in each of two Arms.

As an exploratory evaluation, a subject will be considered to be an immunological responder, if at any of two consecutive post-vaccine time points (i.e., Weeks A13, 19 and A25):

- 1. Presence of a CD4+ or CD8+ T cell population which shows positive tetramer staining against any of IMA950 antigens.
- 2. Four-fold increase of the frequency of the tetramer positive cells within the CD4+ or CD8+ T cell population at the considered post-vaccination time points versus the prevaccination time point.

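### Cheap improvement, not an error: randomisation is stratified by newly diagnosed versus recurrent disease, but the primary immunogenicity test in 12.1.2 ignores the stratum

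*Combined protocol and SAP*

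**What the plan says.** Section 4.1 (Registration and Randomization): "The randomization will take place in a 1:1 ratio between the two arms with the stratification based on whether the patient is newly diagnosed" or recurrent. The patients before that point are not randomised. "The study is designed with a staggered safety lead-in with the first 3 patients assigned to Arm 2", and if no regimen-limiting toxicity occurs the next three go to Arm 1.

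Section 12.1.2 (Primary Immunogenicity Objective): "The standardized difference between pre- and post-vaccine PBMC will be compared between arms via a two-sample" Student's t test. If its assumptions fail and "the data cannot be transformed in such a way that the assumptions are met, a Wilcoxon Rank Sum test will be used". The power statement reads "Based on a one-sided two-sample equal variance t-test, the statistical power will be 80% with 15 patients per arm", for a difference of 0.8, an SD of 1.0 in both arms and a significance level of 0.10. Neither test has a stratum term.

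Section 8.1 describes the primary comparison differently, "by comparing the sum of post-vaccine tetramer+ percentages of all time points from all patients in each of two Arms", and also without the stratum.

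Section 2.7, on the team's earlier peptide vaccine studies: "Cohort 1 patients demonstrated significantly higher" IFN-γ responses than Cohort 3. Cohort 1 was newly diagnosed. Cohort 3 is not defined, but by context it is the recurrent study.

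**The concern.** The design treats newly diagnosed versus recurrent disease as important enough to balance on, and the primary analysis then leaves it out. If the factor is related to immune response, balancing removes its contribution from the arm difference. The plain t test still counts that contribution as noise in the standard error. The result is a test that rejects less often than its nominal 10% under the null and gives up some power under the alternative.

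With 15 patients per arm and accrual planned at one to two patients a month, power is expensive to buy with patients. The stratum is already recorded for every randomised patient, so using it needs no new data. What is at stake is efficiency, not validity.

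**Working it through.** **Inputs from Section 12.1.2.** n = 15 per arm, difference 0.8, SD 1.0, one-sided alpha 0.10.

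**Assumptions (not in the documents).** The lead-in patients count among the 15 per arm. The strata are mixed 50:50, with blocks of 4 within stratum. The total SD of the difference stays at 1. The stratum effect d is in within-stratum SDs and is shown over a range. The undefined standardized difference is read as one pre/post difference per patient.

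**1. The stated power.** Noncentrality = 0.8 / (1.0 × √(2/15)) = 2.191, on 28 df with critical value 1.313. Power = 0.810. The stated 80% reproduces.

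**2. What the stratum term does.** With stratum share p, the stratum explains R² = d²p(1−p) / (1 + d²p(1−p)) of the variance. The residual SD falls to √(1−R²), and one df is spent (27 left). With p = 0.5 and arms exactly balanced within stratum:

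| d | R² | residual SD | noncentrality | power, arm + stratum |
|---|---|---|---|---|
| 0 | 0 | 1.000 | 2.191 | 0.809 |
| 0.5 | 0.059 | 0.970 | 2.258 | 0.827 |
| 1.0 | 0.200 | 0.894 | 2.449 | 0.871 |
| 1.5 | 0.360 | 0.800 | 2.739 | 0.921 |

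**3. Why the plain t test is conservative.** Under exact balance the arm difference varies only with the residual SD, but the t test divides by the total SD. At d = 1.0 its effective critical value is about 1.313 / 0.894 = 1.468, for which the one-sided tail on 28 df is about 0.077 instead of 0.10.

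**4. Simulation with the actual allocation.** Three plus three lead-in patients were assigned without regard to stratum, then blocks of 4 were used within stratum:

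| d | planned t, one-sided error | planned t, power | change with arm + stratum (points) |
|---|---|---|---|
| 0 | 0.10 | 0.809 | about -0.3 |
| 0.5 | 0.096 | 0.814 | about +1.0 |
| 1.0 | 0.083 | 0.828 | about +4.1 |
| 1.5 | 0.067 | 0.843 | about +7.6 |

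Adding the change to the planned power gives 0.806, 0.824, 0.869 and 0.919, within 0.3 point of step 2. A separate simulation at d = 1.0 gave 0.823 against 0.865, with planned-test error 0.081.

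**5. Cost when the stratum does nothing (d = 0).** About 0.3 point in the base setting. With a 10:90 mix, power goes from 0.813 to 0.806 (0.7 point). With 24 patients in total, it goes from 0.738 to 0.732 (0.6 point).

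**6. The fallback.** Van Elteren minus plain Wilcoxon, in points, at d = 0 / 0.5 / 1.0 / 1.5:
- normal data: about -1.4 / 0 / +3.5 / +8.2
- heavy-tailed data (t with 3 df): -0.8 / +0.8 / +4.7 / +8.3
- skewed data (lognormal): -0.6 / +0.7 / +4.7 / +8.7

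**7. How large might d be?** Section 2.7 reports robust responses in 10 patients of Cohort 1 (13 enrolled) and 4 of Cohort 3 (10 enrolled in the recurrent study). Evaluable numbers are not given. Probit(10/13) − probit(4/10) = 0.736 + 0.253 = 0.99, with standard error 0.56 and 95% interval -0.10 to 2.08. The interval includes zero and spans every row above.

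**The case against.** The strongest reply is that nothing here is wrong. The t test is valid, its power statement is right, any distortion of its error rate is on the safe side, and a pilot may choose a simple test. All of that stands, and it is why the point is offered as an improvement.

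The second reply is that the gain rests on an unknown. This also stands. Section 2.7 supports the direction only: the earlier studies used different peptides and an ELISPOT readout, and their newly diagnosed patients were restricted to high-risk disease, a restriction that Section 3.1 does not impose. At effects of 0 to 0.5 SD the change is only -0.3 to +1 point.

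A reader might go further and conclude that the day -23 value should enter as a covariate too, since a PBMC sample "is obtained on the day of the 1st vaccine" (Protocol Synopsis, pre-surgical phase). The documents do not support making that the main fix. When the baseline slope is already 1, so that subtraction is the best use of the baseline, the fuller model costs about 1.5 to 2 points at a stratum effect of 0. Of the settings examined, it clearly beats stratum adjustment alone only with equal pre and post SDs and a correlation of 0.5, a pattern for which the documents give no evidence. It would also replace the pre/post outcome of 12.1.2 with a post-vaccine summary, while 12.1.2 and 8.1 still disagree on the outcome.

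**Conclusion.** The point holds as a low-cost efficiency improvement. If the stratum predicts response, the planned test is conservative (one-sided error about 0.083 at a 1 SD effect) and loses about 4 points of power against a stratified analysis of the same data. At 1.5 SD the loss is about 7.6 points; at 0.5 SD it is about 1. If the stratum is unrelated to response, stratifying loses a fraction of a point. These figures rest on the assumptions listed in the working, above all 15 per arm including the lead-in, which Section 4.1 does not settle, and a 50:50 mix.

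Two stronger readings are not supported. A reader might infer that the trial is underpowered or its primary test invalid. It is neither: the planned test reaches about 80% power or more in the base design at every stratum effect computed. A reader might also infer an expected gain of about 4 points from the earlier cohorts, because 0.99 lies next to the 1.0 row. The interval of -0.10 to 2.08 rules out choosing any one row.

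**What to change.** In 12.1.2, replace the two-sample t test and its fallback with wording such as:

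> The per-patient pre/post difference will be analysed by a linear model with terms for arm and randomisation stratum (newly diagnosed or recurrent). Arm will be tested one-sided at the 0.10 level. Should the model assumptions fail even on a transformed scale, a van Elteren test stratified by newly diagnosed or recurrent disease will replace the Wilcoxon rank-sum test.

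Lead-in patients who are analysed should be classified by the same factor. The change should be made before any comparison between arms is run.

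Cost: SAP wording, no new data and no change in sample size. The model spends one degree of freedom, roughly 0.3 to 0.7 point of power in the settings examined if the stratum has no effect, and more with a more uneven mix or fewer patients. The van Elteren fallback costs about 0.6 to 1.5 points against Wilcoxon in the same case.

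Adding the day -23 value as a covariate is optional. It should be considered only after 8.1 and 12.1.2 agree on one per-patient outcome, which is a separate matter.
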